10.3 Primary Endpoint and Analysis

10.3.1 Part 1, Dose-Escalation

The primary objective of the dose-escalation part is to assess the safety and tolerability of Pan-HER. This will be assessed by the primary endpoint for Part 1: occurrence of DLTs during Cycle 1 for each of the Pan-HER dose regimens.

All DLT events will be listed by dose cohort and patient. A summary table of DLTs across dose cohorts by System Organ Class (SOC) and preferred term will be presented, if applicable. The summaries will include number of DLTs, number, and percentages of patients experiencing a DLT. The definition of a DLT is included in **Section 9.5.1**.

The MTD is defined as the highest dose with a maximum of 1 out of 6 patients experiencing a DLT. The MTD may or may not be found within the dose levels tested. Based on an overall evaluation of the dose-escalation part, the RP2D to be used in Part 2 will be selected. The RP2D may be equal to or lower than the MTD.

10.3.2 Part 2, Dose-Expansion

The primary objective of Part 2 is to evaluate the antitumor effect of Pan-HER when administered at the RP2D and regimen to patients with advanced epithelial malignancies without available therapeutic options. Four (4) dose-expansion cohorts will be evaluated. This will be assessed by the primary endpoint for Part 2: documented OR, defined as documented PR or CR assessed by RECIST v1.1 at any time during trial participation, with radiologic evaluation to be performed locally.

Number and percentages of patients with documented OR will be presented including corresponding 95% exact Clopper-Pearson Confidence Intervals (CI) for binomial proportion. The summaries will be presented for each tumor type separately.

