8.3 Disease Assessments

8.3.1 Disease Status Evaluation by CT or MRI

The anti-tumor activity of Pan-HER will be assessed by the Investigator, or qualified designee, according to RECIST v1.1. Refer to **Appendix 1**.

Patients will undergo imaging by CT or MRI of neck, chest, abdomen and pelvis as indicated based on tumor type and clinical judgment in order to follow the underlying malignancy. The use of CT or MRI must be consistent per patient throughout the trial. Use of contrast is preferred but is at the discretion of the Investigator, as medically indicated.

Screening

Note: A CT/MRI performed within 28 days prior to Day 1 may be used for evaluation of eligibility and as baseline scan, provided that the CT/MRI has been performed according to the protocol requirements.

Confidential Page 78 of 156

- End of Cycle 2 and end of every second cycle thereafter, i.e., Cycle 4, 6, 8 etc.

 Note: End of cycle assessments may be conducted at any time during the week prior to Day 1 of the next cycle.
- Suspected PD (as soon as possible)
- Confirmation of response, to be performed 28 (+7) days after the first assessment of CR/PR
- EOT (if >3 weeks since previous CT/MRI)
- At 1M FUP (if PD was not documented before or at EOT)

If PD is documented at any time, no further disease assessments will be required. Patients with documented PD will be discontinued from Pan-HER so that alternative management of their malignancy may be considered.

To be assigned a status of confirmed PR or CR, changes in disease status must be confirmed by repeat imaging studies performed no less than 28 days (4 weeks) after the criteria for response are first met. In the case of SD, follow-up measurements must have met the SD criteria at least once after trial entry at a minimal interval in general no less than 6-8 weeks from first dose of Pan-HER.

Imaging data (imaging studies and derived assessments) will be stored by the trial sites and will be available upon request for potential review by the Sponsor or an independent radiology reviewer. For Part 2 only: In addition, imaging studies will be sent to an imaging facility for storage to ensure central availability and readiness for read at a future time upon Sponsor or Health Authority (HA) request.

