10. STATISTICS

10.1 Sample Size Considerations

The primary endpoint of Part 1 is occurrence of DLTs during Cycle 1 for each of the Pan-HER dosing regimens. The number of enrolled patients will depend on the extent of observed DLTs independently in each cohort. Please refer to **Section 7.1.3.2** for a description of planned dose levels and decision points for dose-escalation. Based on the dose-escalation design, it is planned to enroll approximately 34 patients during the dose-escalation part of the trial.

In Part 2 of the trial, the primary endpoint is documented OR, defined as documented PR or CR assessed by RECIST v1.1 at any time during trial participation, with radiologic evaluation to be performed locally.

During Part 2, it is planned to enroll and treat approximately 100 patients. The planned number of patients to be enrolled might be adjusted when the 4 dose-expansion cohorts (i.e., based on defined molecular profiles(s) and tumor types) have been selected. The protocol amendment defining the dose-expansion cohorts will contain a detailed sample size calculation covering the four expansion cohorts, including expected range of OR.

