Progressive Disease (PD)	At least a 20% increase in the sum of diameters of target lesions, taking as reference the smallest sum on study (this includes the baseline sum if that is the smallest on study). In addition to the relative increase of 20%, the sum must also demonstrate an absolute increase of at least 5 mm. (Note: the appearance of one or more new lesions is also considered progression)
Stable Disease (SD)	Neither sufficient shrinkage to qualify for PR nor sufficient increase to qualify for PD, taking as reference the smallest sum diameters while on study

Table 15 Response Criteria for Evaluation of Non-Target Lesions

	Evaluation of Target Lesions
Complete Response (CR)	Disappearance of all non-target lesions and normalization of tumor marker level. All lymph nodes must be non-pathological in size (<10 mm short axis)
Progressive Disease (PD)	Unequivocal progression of existing non-target lesions. (Note: the appearance of one or more new lesions is also considered progression)
Non-CR/Non-PD	Persistence of one or more non-target lesion(s) and/or maintenance of tumor marker level above the normal limits

Confidential Page 121 of 156

Evaluation of Best Overall Response

It is assumed that at each protocol specified time point, a response assessment occurs. **Table 16** provides a summary of the overall response status calculation at each time point for patients who have measurable disease at baseline

 Table 16
 Overall Response Status for Patients with Baseline Measurable Disease

Target Lesions	Non-target Lesions	New	Overall
		Lesions	Response
CR	CR	No	CR
CR	Non-CR/Non-PD	No	PR
CR	Not evaluated	No	PR
PR	Non-PD or not all evaluated	No	PR
SD	Non-PD or not all evaluated	No	SD
Not all evaluated	Non-PD	No	NE
PD	Any	Yes or No	PD
Any	PD	Yes or No	PD
Any	Any	Yes	PD

Abbreviation: CR, complete response; NE, not evaluable; PD, progressive disease; PR, partial response; SD, stable disease

The best overall response is determined once all the data for the patient is known.

Best response determination in trials where confirmation of CR or PR is NOT required:

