CR	CR	No	CR
CR	Non-CR/non-PD	No	PR
CR	Not evaluated	No	PR
PR	Non-PD or not all evaluated	No	PR
SD	Non-PD or not all evaluated	No	SD
Not all evaluated	Non-PD	No	NE
PD	Any	Yes or No	PD
Any	PD	Yes or No	PD
Any	Any	Yes	PD

CR = complete response, PR = partial response, SD = stable disease, PD = progressive disease, and NE = inevaluable.

Table 2 – Time point response: patients with non-target disease only.

Non-target lesions	New lesions	Overall response
CR	No	CR
Non-CR/non-PD	No	Non-CR/non-PD ^a
Not all evaluated	No	NE
Unequivocal PD	Yes or No	PD
Any	Yes	PD

CR = complete response, PD = progressive disease, and NE = inevaluable.
 a 'Non-CR/non-PD' is preferred over 'stable disease' for non-target disease since SD is increasingly used as endpoint for assessment of efficacy in some trials so to assign this category when no lesions can be measured is not advised.

- Confirmed Best Overall Response (BOR) by RECIST v1.1.

Per RECIST 1.1[1]:

'the best overall response is the best response recorded from the start of the study treatment until the end of treatment taking into account any requirement for confirmation.'
'Specifically, in non-randomised trials where response is the primary endpoint, confirmation of PR or CR is needed to deem either one the 'best overall response'.' *'Best response determination in trials where confirmation of complete or partial response is*

PAREXEL International
Statistical Analysis Plan Template for Early Phase Studies

Symphogen A/S
Sym013-01

required: Complete or partial responses may be claimed only if the criteria for each are met at a subsequent time point as specified in the protocol (generally 4 weeks later). In this circumstance, the best overall response can be interpreted as in Table 3.'

Table 3 of above-mentioned paper [1] is reported below and will be used to derive confirmed Best Overall Responses. In this study a minimum SD duration of 6 week will be used as criterium to confirm SD as Best Overall Response.

Table 3 – Best overall response when confirmation of CR and PR required.

Overall response First time point	Overall response Subsequent time point	BEST overall response
CR	CR	CR
CR	PR	SD, PD or PR ^a
CR	SD	SD provided minimum criteria for SD duration met, otherwise, PD
CR	PD	SD provided minimum criteria for SD duration met, otherwise, PD
CR	NE	SD provided minimum criteria for SD duration met, otherwise NE
PR	CR	PR
PR	PR	PR
PR	SD	SD
PR	PD	SD provided minimum criteria for SD duration met, otherwise, PD

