PR	NE	SD provided minimum criteria for SD duration met, otherwise NE
NE	NE	NE

CR = complete response, PR = partial response, SD = stable disease, PD = progressive disease, and NE = inevaluable.

a If a CR is truly met at first time point, then any disease seen at a subsequent time point, even disease meeting PR criteria relative to baseline, makes the disease PD at that point (since disease must have reappeared after CR). Best response would depend on whether minimum duration for SD was met. However, sometimes 'CR' may be claimed when subsequent scans suggest small lesions were likely still present and in fact the patient had PR, not CR at the first time point. Under these circumstances, the original CR should be changed to PR and the best response is PR.

Patients with non-target disease only, may have a time point response of NON-CR/NON-PD, these responses will be included in the count of SD.

Determinations of Best Overall Responses derived as described will be reviewed by Symphogen and PAREXEL on a patient by patient basis across time.

- Unconfirmed BOR by RECIST v1.1:

Per RECIST 1.1 [1]: in cases where confirmation of complete or partial response is not required the Best response is defined as the best response across all time points (for example, a patient who has SD at first assessment, PR at second assessment, and PD on last assessment has a best overall response of PR). When SD is believed to be best unconfirmed response, it must also meet the protocol specified minimum time from baseline.

PAREXEL International
Statistical Analysis Plan Template for Early Phase Studies

Symphegen A/S
Sym013-01

Patients with non-target disease only, may have a time point response of NON-CR/NON-PD, these responses will be included in the count of SD.

- Documented objective response (OR) confirmed and unconfirmed, based on determination of confirmed and unconfirmed best overall response (BOR) per RECIST v1.1.

Confirmed OR is defined as the percentage of patients who had confirmed CR or PR.

Unconfirmed OR is defined as the percentage of patients who had unconfirmed CR or PR.

'The duration of overall response is measured from the time measurement criteria are first met for CR/PR (whichever is first recorded) until the first date that recurrent or progressive disease is objectively documented (taking as reference for progressive disease the smallest measurements recorded on study). ' [1].

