4.10.2.1 Anti-Tumor Response according to RECIST v1.1

The following anti-tumor response endpoints will be measured in Part 1:

- Confirmed and unconfirmed BOR by RECIST v1.1 will be listed and summarized by dose regimen and dose level received using frequency distribution for the categories CR, PR, SD, PD, and Not Evaluable.
- Number and percentage of patients with documented confirmed and unconfirmed OR will be summarized by dose regimen and dose level using frequency distribution with the corresponding 95% exact Clopper-Pearson Confidence Intervals (CI) for binomial proportion. All documented ORs will be listed including duration (weeks) of response.
- Patients in DCR will be listed and summarized by dose regimen and dose level using frequency distribution with the corresponding 95% exact Clopper-Pearson Confidence Intervals (CI) for binomial proportion.
- Time to Progression (TTP)

PAREXEL International
Statistical Analysis Plan Template for Early Phase Studies

Symphogen A/S
Sym013-01

The median TTP, as well as 26 weeks and 52 weeks TTP rates and the corresponding 95% CIs will be estimated using the product-limit method and presented using a Kaplan-Meier plot. Number and percent of censored patients will be presented, also number and percent of patients censored for death will be presented.

- Changes in sum of diameters of target lesions from baseline to end of trial participation
Changes in the sum of diameters of target lesions from baseline to end of trial participation will be listed as percentage and absolute value, the best change (i.e., largest reduction or smallest increase) will be identified and presented using summary table and plotted with a waterfall plot. Change in sum of diameters will also be presented by primary tumor type.
- Results of the tumor evaluation by CT/MRI for target lesions, non-target lesions and timepoint tumor response will be listed, as well as derived target and non-target time point responses.

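### The Part 2 primary endpoint, documented OR, does not require a confirmed response; separately, the SAP does not say which form of OR is the main one in Part 1, and its duration of response needs no confirmation

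*Protocol*

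**What the plan says.** **Part 2, primary endpoint.** Protocol 10.3.2 defines it as "documented OR, defined as documented PR or CR assessed by RECIST v1.1 at any time during trial participation", with radiology read locally; the synopsis and 10.1 give the same definition. The analysis is descriptive: "Number and percentages of patients with documented OR will be presented including corresponding 95% exact Clopper-Pearson Confidence Intervals (CI) for binomial proportion". On size, 10.1 says only "During Part 2, it is planned to enroll and treat approximately 100 patients", over four cohorts. It leaves the expected OR and the sample size calculation to a later amendment.

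**Confirmation elsewhere in the protocol.** Section 8.3.1 and the footnotes to Tables 2 and 3 schedule a repeat CT/MRI 28 (+7) days after the first CR or PR. Section 8.3.1 adds: "To be assigned a status of confirmed PR or CR, changes in disease status must be confirmed by repeat imaging studies", at least 28 days after the criteria are first met. Appendix 1 gives one rule headed "Best response determination in trials where confirmation of CR or PR is NOT required" and then the rule for trials where confirmation is required (Table 17). It does not say which applies.

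**SAP.** Section 1 drops every Part 2 analysis, and 4.14 records that Part 2 did not take place. Section 3.2 keeps documented OR as a Part 1 secondary efficacy endpoint, and 3.2.1.1 derives it as "Documented objective response (OR) confirmed and unconfirmed, based on determination of confirmed and unconfirmed best overall response (BOR) per RECIST v1.1". Section 4.10.2.1 summarises both forms with exact 95% intervals and then says "All documented ORs will be listed including duration (weeks) of response". DCR is based on confirmed best overall response only. In setting out confirmed response, 3.2.1.1 cites RECIST: "in non-randomised trials where response is the primary endpoint, confirmation of PR or CR is needed to deem either one" the best overall response.

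**The concern.** Part 2 is single-arm, open-label and locally read, with response as its primary endpoint. In that setting a confirmation requirement guards against a measurement fluctuation being counted as a response. Confirmed responders are a subset of unconfirmed responders, so leaving out confirmation can only raise the rate or leave it unchanged. The protocol collects the scan needed for confirmation and defines confirmed status, but never ties that status to the endpoint.

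At stake is the antitumour statement, which is the Part 2 primary objective. In Part 1 the stake is smaller. Secondary objective 6 is a preliminary look at antitumour effect. Two OR figures will be available for it with no stated order of precedence, and the duration listing can include responses seen only once.

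**Working it through.** The documents state no response rate, power or threshold for OR, so there is no plan figure to reproduce. The check is a comparison of texts, followed by illustrations on stated assumptions.

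**1. Which rule governs documented OR?**

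| Place | Content | Settles confirmation for documented OR? |
|---|---|---|
| Protocol 10.3.2, 10.1, synopsis | PR or CR at any time | No; confirmation is not mentioned |
| Protocol 8.3.1 | Defines confirmed PR/CR | No; not linked to documented OR |
| Protocol Appendix 1 | Both best-response rules | No; no choice made |
| SAP 3.2.1.1, RECIST citation | Confirmation needed if response is primary in a non-randomised trial | Points to confirmation for Part 2; its condition is not met in Part 1, where DLT is primary |
| SAP 3.2.1.1, 4.10.2.1 | Both forms, labelled (Part 1) | No; neither named as main |

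**2. Size in Part 2 (illustration only).** Assumption: 100/4 = 25 patients per cohort; the current text gives no split. Each reclassified patient moves the rate by 1/25 = 4 points. Clopper-Pearson 95% intervals:

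- 5/25 (all counted): 20.0% (6.8 to 40.7)
- 4/25 (one of five not confirmed): 16.0% (4.5 to 36.1)
- 3/25 (two of five not confirmed): 12.0% (2.5 to 31.2)

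Let u be the unconfirmed rate and f the share of responses not confirmed; both are assumptions. The chance that a cohort contains at least one patient who responds only under the unconfirmed reading is 1 − (1 − u·f)^25:

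- u = 12%, f = 10%: 1 − 0.988^25 = 26%
- u = 20%, f = 20%: 1 − 0.96^25 = 64%; the expected rate falls from 20% to 16%
- u = 28%, f = 40%: 1 − 0.888^25 = 95%

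**3. How large might the gap be?** A simulation used scans at weeks 8, 16 and 24, a confirmatory scan four weeks later, and follow-up stopped at a 20% rise from nadir. None of the following inputs comes from the documents: log measurement SD 0.08 to 0.15; mean growth 0 to 10% per 8 weeks; between-patient SD 0.10 to 0.20. Across nine settings the ratio of unconfirmed to confirmed rate ran from 1.08 to 1.89, and seven of the nine were about 1.3 or less. So 5 against 4 (ratio 1.25) is a more typical illustration than 5 against 3 (ratio 1.67).

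**4. A Part 1 patient under the SAP's own rules.** Take a PR on treatment day 56 (end of Cycle 2) and PD at the confirmatory scan on day 84.

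- Unconfirmed best response: PR, so an unconfirmed responder.
- Confirmed best response (SAP Table 3, PR then PD): SD, because the 6-week minimum is met.
- TTP = (84 − 1 + 1)/7 = 12.0 weeks. This is below the 16 weeks of SD that DCR needs, so the patient is not disease-controlled.
- Duration of response = (84 − 56 + 1)/7 = 4.1 weeks. The formula runs from first CR/PR to PD and has no confirmation condition.

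Table 14.2.4.1, which holds best response, OR and DCR, could therefore count this patient as an unconfirmed responder but not as disease-controlled. The listing of documented ORs could also show a 4.1-week response.

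**5. Part 1 scale.** Protocol 3.2.4.1 reports 19 patients at Amendment 6, in cohorts of 1 to 7. If all count in the denominator, one reclassified patient moves a cohort of 7 by 1/7 = 14.3 points and the pooled 19 by 1/19 = 5.3 points. Final numbers are not in the SAP.

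**The case against.** The strongest reply on Part 2 is that the at-any-time phrase sets the observation window while RECIST v1.1 supplies the criteria. RECIST, as the SAP quotes it, asks for confirmation in this design, and the scan is mandated. This stands to a degree: the protocol permits single-scan responses but does not clearly direct that they be counted. It does not close the gap, because Appendix 1 leaves both rules open. Part 2 also needed a further amendment before opening, and that could have settled the point.

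For Part 1, a reader might infer three stronger things that the documents do not support:

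- *The SAP computes the Part 2 primary endpoint in two ways.* It does not. Part 2 is omitted, and the two-form OR is the Part 1 secondary endpoint of the same name.
- *An unconfirmed rate could silently pass as the response rate.* Both forms are defined, labelled and summarised together, and response by visit is listed. A reader can see which responses were confirmed.
- *RECIST, as quoted, obliges confirmation in Part 1.* The sentence is conditional on response being the primary endpoint. In Part 1 that is DLT, so reporting unconfirmed OR there does not depart from the quoted text.

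It is also fair that Part 1 OR is descriptive, with no test or threshold. None of this reaches the duration formula and listing, which do not say whether they take confirmed or unconfirmed responses.

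**Conclusion.** The point holds in two separate parts.

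1. **Part 2.** The primary endpoint as worded does not require confirmation, in a single-arm, locally read design for which the RECIST text quoted in the SAP calls for it. The possible error runs one way, upwards. At an assumed 25 per cohort it is 4 points per unconfirmed responder. The intervals, chances and ratios above are illustrations for Part 2 only and rest on assumptions from outside the documents.
2. **Part 1.** This is a smaller gap. Neither form is named as documented OR, and duration of response carries no confirmation condition. SAP 4.14 lists other changes from the protocol but not the split into two forms.

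Because Part 2 did not open, the live consequence is limited to the descriptive Part 1 OR statement and the duration listing. The Part 2 wording matters if the protocol text is used again.

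**What to change.** **Protocol.** In 10.3.2, 10.1 and the synopsis, define documented OR as confirmed PR or CR per 8.3.1, that is, with repeat imaging at least 28 days after the criteria are first met. In Appendix 1, state that the confirmation-required rule (Table 17) applies.

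**SAP.** In 3.2.1.1 and 4.10.2.1, name confirmed OR as the main analysis and unconfirmed OR as supportive. Give duration of response for confirmed responders, and list unconfirmed responders separately.

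**Cost.** Wording only: the confirmatory scan is already scheduled and both forms are already planned. The downside is a slightly lower headline response rate. With Part 2 closed, the SAP sentences are the part that still has an effect.

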10.4 Secondary and Exploratory Endpoint and Analysis

All statistical analyses of the secondary and exploratory endpoints for both phases will be descriptive unless otherwise specified. Details will be specified in a separate statistical analysis plan.

In the following sections, 'cohort' refers to dose cohort for Part 1 and tumor type for Part 2. Thus, summaries by trial part and cohort will be presented by dose cohorts within Part 1 and tumor types within Part 2.

Confidential Page 96 of 156

